### **8.2.2 Change in body surface area affected by psoriasis**

The percentage BSA (0 to 100%) affected by psoriasis will be listed by PS0016 randomized treatment, by subject and visit including the percentage change from PS0016 Baseline. Missing data will not be imputed for the listing.

Descriptive statistics will be presented by PS0016 randomized treatment group and overall, by visit for both absolute values and percentage changes from Baseline.

Missing data for the tabulations will be imputed as described in [Section 4.2.1.2](#). Tabulations (absolute values and percentage change from PS0016 Baseline) will be repeated using observed cases for both treatment assignments and will include the category missing.

### 8.2.3 Investigator's Global Assessment

The results of the IGA will be listed by PS0016 randomized treatment group, subject and visit. A clinical response with regard to the IGA is defined as clear (0) or almost clear (1) with at least a 2 category improvement from Baseline. Subjects achieving a clinical response will be flagged in the listing at relevant visit timepoints. Missing data will not be imputed for the listing.

The number and percentage of subjects achieving an IGA response at each PS0018 visit will be summarized by PS0016 randomized treatment group and overall. The 95% CI for the percentage of responders will be included, calculated using a Wilson approximation. For the purpose of the tabulation the lower and upper 95% confidence limits for the percentage of responders will be truncated at 0 and 100% respectively.

Missing data will be imputed using NRI as described in [Section 4.2.1.3](#). The tabulation will also be repeated using observed cases for both treatment assignments and will include a category for missing data; those who discontinue will be counted in the missing category for this tabulation where applicable. For the tabulation based on observed cases, the denominator for the percentage of responders and non-responders, will be the number of subjects with nonmissing data at the visit.

Shift tables will be presented for the IGA score, by PS0016 randomized treatment group and overall, at each PS0018 visit, compared to the PS0016 Baseline score.

In addition, a frequency table will be presented showing the number and percentage of subjects with each specific IGA score at each visit by PS0016 randomized treatment group. Both tabulations will include a category for missing data. The denominator for the percentages will be the number of subjects in the FAS, for each PS0016 randomized treatment group. No imputation for missing values will be done for these analyses.

### 8.2.4 Hospital Anxiety and Depression Scale

The HADS scores for anxiety HADS-A and depression HADS-D each range from 0 to 21 with higher scores indicating worse state. A score below 8 is considered to be normal whereas a score of 15 and above is considered severe (Snaith and Zigmond, 1994). The individual items, associated item scores and calculation rules for the anxiety and depression domains are provided in [Section 8.1.3](#).

The results of the HADS will be listed by PS0016 randomized treatment group, subject and visit including the individual item responses and the derived domain scores for HADS-A and HADS-D. Changes from Baseline will be calculated based on the domain scores only, and will be included in the listing. A Glossary will also be included.

Descriptive statistics will be presented by PS0016 randomized treatment group and overall, by visit for both absolute values and changes from Baseline, separately for each domain HADS-A and HADS-D. Missing data will be imputed as defined in [Section 4.2.1.3](#) and supportive summaries of observed cases will also be included for both treatment assignments.

The number and percentage of subjects with scores categories  $<8$ ,  $\geq 8$  to  $<11$ ,  $\geq 11$  and missing for the HADS-A and HADS-D will be summarized by PS0016 randomized treatment group and overall at each visit based on observed cases. The percentages will be based on the number of available observations at each visit.

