### 4.4 Efficacy variables

Change from Baseline variables will be defined relative to the Baseline measurement from PS0016.

The efficacy variables are listed below and will be evaluated at all scheduled visits in accordance with the schedule of assessments in [Table 5–1](#).

- PASI50, PASI75, PASI90, and PASI100 response
- IGA response (Clear or Almost Clear with at least a 2 category improvement from Baseline on a 5-point scale)
- Absolute and percent change from Baseline in PASI score
- Shift from Baseline in IGA score
- Absolute and percent change from Baseline in the BSA affected by psoriasis
- Change from Baseline in the HADS Anxiety (HADS-A) and Depression (HADS-D) scores
- Percentage of subjects with scores below 8 in HADS-A and HADS-D (subjects with normal scores)

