    - Persistent is defined as lasting 28 days or more, which spans at least 2 scheduled injections.

10. Subject has a clinical laboratory value meeting the following criteria:

- CTCAE Grade 3 and above: subjects must be withdrawn regardless of relationship to study drug or duration of event.
- CTCAE Grade 2
  - Subjects may remain in the study if the event is transient. If a subject has a Grade 2 laboratory abnormality, a retest is required within 1 to 2 weeks at a scheduled or unscheduled visit. If the repeat value is below Grade 2, the subject may receive the next scheduled study treatment. If the value on the repeat is still Grade 2 or above, a second repeat test must be performed and results made available prior to the next scheduled study treatment. If this second repeat value is still Grade 2 or above, the subject must be withdrawn.

11. Subject has active suicidal ideation as indicated by a positive response (“Yes”) to questions 4 or 5 or to the suicidal behavior questions of the “Since Last Visit” version of the self-rated Columbia-Suicide Severity Rating Scale (C-SSRS). The subject should be referred immediately to a Mental Healthcare Professional and must be withdrawn from the study.

12. Subjects with a HADS-D score  $\geq 15$  must be withdrawn. Any subject who develops a HADS-D score of  $>10$  during the study should be referred immediately to a Mental Healthcare Professional for further evaluation and potential withdrawal by the Investigator.

13. Subject does not achieve a PASI50 at Week 12 or later following open-label treatment in PS0018.

14. Subjects with newly diagnosed Inflammatory Bowel Disease (IBD) or with IBD flares during the study must:

- Be referred, as appropriate, to a healthcare professional treating IBD, such as a gastroenterologist
- Discontinue the IMP and be followed-up until resolution of active IBD symptoms

If IBD flares increase in severity or frequency during the study, the Investigator should use clinical judgment in deciding whether the subject should continue in the study and contact the Medical Monitor and UCB study physician to confirm the subject's suitability for continued participation in the study.

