### **14.5 Planned efficacy analyses**

Efficacy variables will be summarized based on the FAS. The summaries described in this section will provide data on maintenance of effect of open-label bimekizumab over 48 weeks. Additionally, it will allow an assessment of the impact of dose adjustments on efficacy results.

Responder efficacy variables (PASI50, PASI75, PASI90, PASI100, IGA score of 0 or 1, and HADS normal scores) will be summarized descriptively using counts and percentages by scheduled visit and PS0016 randomized treatment group and overall. The PASI responder variables are derived relative to the PS0016 Baseline. Missing data will be handled by using nonresponder imputation (NRI), meaning that subjects that discontinue early or who have missing data at a given time point are imputed as though they did not achieve the given response. Supportive summaries will be based on observed case data.

Continuous efficacy variables based on the change from Baseline (PASI, BSA, and HADS) will be summarized using descriptive statistics by scheduled visit and PS0016 randomized treatment group and overall. The table presentations will display descriptive statistics for the PS0016 Baseline and the observed and change from PS0016 Baseline results by scheduled visit for PS0018. Figures for selected variables will also be generated in order to demonstrate the kinetics of response over time. Missing data will be handled by using multiple imputation (MI) via the

Markov-Chain Monte Carlo (MCMC) method. Supportive summaries will be based on observed case data.

In addition to the summaries described above, the impact of dose adjustment on efficacy will be considered. This will be done primarily by summarizing efficacy variables by the 3 adjuster groups as defined in [Section 14.2.2](#). Furthermore, a supportive analysis specifically for single adjusters will be performed in which PASI score will be summarized by visit, where Baseline is recalibrated for each individual subject and defined as the visit where the bimekizumab 320mg Q4W dose is initiated. The visits summarized will be in weeks relative to when the 320mg Q4W dose was started as opposed to the scheduled week of the PS0018 assessment. These summaries will be based on observed data only.

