### **4.2 Handling of dropouts or missing data**

If a subject does not achieve a PASI50 at Week 12 or later during the open-label treatment period then they will be withdrawn from the study, in order to provide the subjects with alternative therapy to treat the condition. Therefore, in many cases, missing data due to study treatment discontinuation will occur. For missing continuous data single imputation by means of LOCF will be applied.

Missing data for the binary response variables will be imputed using non responder imputation (NRI), ie subjects with a missing score at a specific visit will be considered as non-responders for the summaries. This will include visits after the point of withdrawal.

Supportive summaries will be based on observed case data and will be repeated for all analyses presented with imputation.

Missing data will be handled as described in the sections below for efficacy, safety and PK results. No other imputations will be performed.

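### SAP 8.2.4 reports HADS normal scores on observed cases only; the protocol's main analysis is non-responder imputation, and the change is not declared

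*SAP*

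**What the plan says.** The percentage of subjects with HADS-A and HADS-D below 8 is a listed efficacy variable (Protocol 4.4, SAP 2.2.4).

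Protocol 14.5 puts it in the same class as the PASI and IGA responses: "Responder efficacy variables (PASI50, PASI75, PASI90, PASI100, IGA score of 0 or 1, and HADS normal scores) will be summarized descriptively". For that class the rule is "Missing data will be handled by using nonresponder imputation (NRI"), which counts subjects who discontinue or lack data at a visit as not having responded. Observed-case summaries are supportive.

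SAP 4.2 repeats the rule in general terms, "Missing data for the binary response variables will be imputed using non responder imputation (NRI"), and extends it to visits after withdrawal. It does not name HADS. The HADS paragraph, SAP 4.2.1.4, gives last observation carried forward (LOCF) for the domain scores and no rule for the normal-score variable.

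SAP 8.2.4 is where the below-8 category is tabulated, together with 8 to below 11, 11 or more, and missing. These counts and percentages are "summarized by PS0016 randomized treatment group and overall at each visit based on observed cases", and the percentages use the observations available at the visit. No NRI version is planned.

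For the continuous HADS scores, SAP 8.2.4 says "Missing data will be imputed as defined in" Section 4.2.1.3, which is the IGA paragraph.

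SAP 3.9 lists the changes from the protocol's analyses. For missing data it declares one, from multiple imputation to LOCF for continuous variables.

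**The concern.** The summary that the protocol calls supportive has become the only one for this variable, and nothing tells the reader so. PASI and IGA responses each keep both an NRI table and an observed-case table (SAP 8.2.1 and 8.2.3). HADS is the one responder variable named in the protocol that loses its NRI table, and no reason is given.

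The choice affects the reported number. SAP 4.2 itself expects discontinuation to cause missing data in many cases. With an observed-case denominator, subjects who have left are removed from the percentage. Under NRI they stay in it as not normal. One withdrawal rule also acts on the outcome: criterion 12 in Protocol 6.3 ("Subjects with a HADS-D score" of 15 or more) takes out subjects who are not normal on HADS-D by definition. Protocol 9.6 lists depression and anxiety, assessed by HADS, among the events for special monitoring, so the percentage may be read for more than efficacy.

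**Working it through.** The documents give no expected HADS-normal percentage, so there is no planned figure to reproduce. The check compares the two definitions.

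**Inputs**
- N = 45, the maximum enrolment (Protocol 14.7, SAP 2.4), used here as the size of the FAS.
- After entry, HADS is scheduled at Weeks 12, 24, 36 and 48 or withdrawal (Protocol Table 5-1).
- W = subjects without a HADS score at a visit, and x = subjects measured and normal. Neither is in the documents. W from 3 to 14 and a starting rate of 80% are assumptions.

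**Step 1: size of the difference**

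Observed-case percentage = x/(N-W). NRI percentage = x/N. For x > 0 their ratio is N/(N-W), whoever is missing.
- W = 3: 45/42 = 1.07
- W = 5: 45/40 = 1.13
- W = 9: 45/36 = 1.25
- W = 14: 45/31 = 1.45

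The gap in percentage points is the observed percentage times W/N. At an observed 80%, 3 missing gives 80 x 3/45 = 5.3 points (NRI 74.7%), and 9 missing gives 80 x 9/45 = 16.0 points (NRI 64.0%).

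**Step 2: movement over time**

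Start with 36 of 45 normal (80.0%). Let 9 leave and the others keep their status.

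| Who leaves | Observed cases | NRI |
|---|---|---|
| 9 non-normal | 36/36 = 100.0% | 36/45 = 80.0% |
| In proportion (7.2 normal, 1.8 not) | 28.8/36 = 80.0% | 28.8/45 = 64.0% |
| 9 normal | 27/36 = 75.0% | 27/45 = 60.0% |

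The observed percentage is above NRI in every row. It rises only if those who leave are less often normal than those who stay.

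**Step 3: which withdrawals are tied to HADS**
- HADS-D of 15 or more (criterion 12): not normal on HADS-D by definition. The subject is counted as 11 or more at the visit where the score is recorded and is absent from later HADS visits. Under SAP 4.4 the early-withdrawal HADS may also be counted at a mapped scheduled visit, so the loss can start one HADS visit later.
- No PASI50 at Week 12 or later (criterion 13): the documents state no link to HADS.
- HADS-A: there is no withdrawal threshold.

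**Step 4: the cross-reference**

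SAP 4.2.1.3 leaves missing IGA scores unimputed and applies NRI to IGA response. Neither gives an imputed value for a mean HADS score. The rule that does is LOCF, in SAP 4.2.1.4.

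**The case against.** - **The SAP may set its own method.** SAP Section 1 says the protocol's analysis applies unless the SAP specifies otherwise, and 8.2.4 does so. SAP 4.2 reaches HADS normal scores only through a general phrase, and 4.2.1.4 gives HADS nothing but LOCF. This stands in part: the explicit NRI requirement is the protocol's alone. But 3.9 is the place where departures are recorded, and this one is not there.
- **Nothing is hidden.** The planned table has a missing category, so a reader can divide the below-8 count by the FAS size. That is true and limits the harm. It still leaves the prespecified main analysis unreported.
- **The percentages do not have to rise.** A reader might infer that they climb as subjects withdraw. Step 2 shows that they can rise, hold or fall. The documents support a selective loss of non-normal subjects only for HADS-D withdrawals.
- **NRI is not the truth.** A reader might call the observed-case figure biased upward. If withdrawal is unrelated to HADS, the observed-case rate is unbiased and NRI understates the proportion normal. What can be said is that the figure is higher than the one the protocol defines.
- **Comparison with PASI and IGA remains possible.** A reader might infer that HADS results cannot be set beside those response rates. Observed-case PASI and IGA tables are also planned, so a like-for-like comparison exists on that basis, though not on NRI, the protocol's main basis.
- **The cross-reference is clerical.** It is, and the intended rule can be recovered from SAP 4.2 and 4.2.1.4. It still needs correcting.

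**Conclusion.** The discrepancy is real and undeclared. For HADS normal scores the SAP drops the NRI analysis that the protocol makes primary for responder variables and keeps only the supportive one. Whenever scores are missing and at least one measured subject is normal, the reported percentage is larger than the protocol's by N/(N-W). For 45 subjects that is 7% in relative terms with 3 missing and 25% with 9. The factor is exact; the numbers missing are assumptions.

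The documents do not support claims of a necessary rise over time, of proven upward bias, or of lost comparability with PASI and IGA. The severity is minor: the variable is one of several descriptive efficacy summaries in an open-label study whose primary objective is safety, and the primary safety analysis is untouched.

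**What to change.** In SAP 8.2.4:
- Add a summary of HADS-A below 8 and HADS-D below 8 at each HADS visit, with NRI and the FAS (by PS0016 group and overall) as denominator, and make it the main table.
- Keep the planned observed-case category table, including its missing category, as supportive.
- Change the reference for imputing the continuous domain scores from 4.2.1.3 to 4.2.1.4.

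Naming HADS normal scores in SAP 4.2.1.4 as subject to NRI would remove the remaining ambiguity. If the sponsor prefers observed cases as the main analysis, the least that is needed is to declare and justify the change in SAP 3.9.

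The cost is a few lines of wording and one extra table. The main percentages will be lower than those now planned at any visit with missing data. No new data collection is needed.

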## 9 PHARMACOKINETICS

There will be no calculation of PK parameters for this study. The analysis of PK data for this study will focus on the concentrations of bimekizumab only.

Individual blood sampling times and concentrations of bimekizumab will be listed by PS0016 randomized treatment group for the SS and will include the actual sampling time in weeks relative to the first PS0018 dose.

Individual concentrations will be summarized by PS0016 randomized treatment group at each scheduled visit based on the PK-PPS, using n, mean, median, SD, minimum, maximum, geometric mean, 95% CI for the geometric mean and geoCV (assuming log-normally distributed data).

Individual concentration versus time (week) profiles will be presented graphically in linear and semi-logarithmic scale with all subjects overlaid on the same plot (spaghetti plots) and separate plots for each treatment group. Geometric mean profiles of bimekizumab will also be presented on both linear and semi-logarithmic scale respectively with and without the corresponding lower and upper limit of the 95% CI for linear and semi-logarithmic plots respectively. Both treatment groups (PS0016 randomized treatment groups) will be overlaid on the same plot. All figures will include the LLOQ on the semi logarithmic plots.

The following rules will apply for PK data listings and summaries:

- Values below the LLOQ will be reported as BLQ
- Descriptive statistics of concentrations will be calculated if at most 1/3 of the individual data points are missing or are not quantifiable ie LLOQ. Values that are BLQ will be replaced by the numerical values of the LLOQ/2 in this instance. However, if  $n \leq 3$  or more than 1/3 of the individual data points are missing or are not quantifiable, then only n, minimum and maximum will be presented. The other descriptive statistics will be left blank.
- The 95% CI for the geometric mean should be left blank if the SD (or equivalently, the geoCV) is 0
- The geoCV will be calculated using the following formula where SD is the standard deviation from the log-transformed data

$$geoCV = [100 \times \sqrt{(e^{SD^2} - 1)}] \quad [9]$$

Additional rules for handling values that are BLQ are described in [Section 4.2.3](#).

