#### **3.2 Secondary objectives**

Secondary objectives of the study are:

- To assess the safety and tolerability of increasing the dose of bimekizumab from 160mg Q4W to 320mg Q4W for subjects with an inadequate response at Week 12
- To assess PK of bimekizumab
- To assess the immunogenicity of bimekizumab
- To assess the efficacy of open-label bimekizumab 160mg Q4W administered over 48 weeks

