### **14.3 Planned PK analyses**

Pharmacokinetic variables will be analyzed for all subjects in the PK-PPS.

Bimekizumab plasma concentrations will be summarized for each treatment at each scheduled visit.

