### **14.4 Planned immunological analyses**

Immunological variables will be analyzed for all subjects in the PK-PPS.

Anti-bimekizumab antibody data will be summarized for each treatment at each scheduled visit.

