### **3.6 Treatment assignment and treatment groups**

Treatment assignment for the SS and PK-PPS will be according to the actual treatment received in PS0018, unless stated otherwise in [Table 3–1](#). Analyses of efficacy data (based on the FAS) will be conducted according to the PS0016 randomized treatment group.

Subjects receiving the incorrect treatment (for example due to a dosing error) at a particular visit will be excluded from the PK-PPS as this would be considered as an important protocol deviation. Subjects may be excluded from the analysis at a particular visit (or visits) only, following discussion at the DEM.

Listings will be presented by subjects as randomized in PS0016. Summaries will be presented by treatment group and overall where applicable. See [Table 3–1](#) for the treatment assignment of the 3 different sets of treatment groups.

---

In the TFLs the treatment groups based on the PS0016 randomized treatment group will be displayed as follows, where BKZ refers to bimekizumab and PBO refers to placebo:

- BKZ 320mg + PBO
- BKZ 320mg
- All Subjects

In the TFLs the treatment groups based on the actual PS0018 treatment received (ie PS0018 dose at onset of event or measurement) will be displayed as follows:

- BKZ 160mg Q4W
- BKZ 320mg Q4W
- All BKZ

Lastly there will be the grouping based on dose adjustment in PS0018 defined as follows:

- Nonadjusters – This group consists of subjects who do not experience a dose adjustment during the study.
- Single adjusters – This group consists of subjects who experience just one dose adjustment during the study. Per the protocol, if just a single adjustment occurs, then that adjustment must go from bimekizumab 160mg Q4W to 320mg Q4W.
- Multiple adjusters – This group consists of subjects who experience more than 1 dose adjustment during the study. This means that the subjects in this group dose adjust from bimekizumab 160mg Q4W to 320mg Q4W and then adjust back to 160mg Q4W (with further dose adjustments possible).

For summary purposes, the single and multiple adjuster groupings will be combined.

The treatment group labels and tabulation requirements for each data type are displayed in [Table 3–1](#) **Error! Reference source not found.**

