**Table 3–1: Treatment group assignment for the TFLs**

TFL group	PS0016 randomized treatment group			PS0018 dose at onset			Dose adjustment group	
	BKZ 320mg + PBO	BKZ 320mg	All Subjects	BKZ 160mg Q4W	BKZ 320mg Q4W	All BKZ	Non- adjuster	Adjuster
Subject disposition	X	X	X					
Protocol deviations	X	X	X					
Demographics	X	X	X					
Medical history	X	X	X					
Prior/concomitant medications	X	X	X					
Compliance	X	X	X					
Exposure				X	X	X		
AEs a	X	X	X	X	X	X	X	X
Safety data (including vital signs, ECGs and laboratory tests)	X	X						
Efficacy (except PASI)	X	X	X					
PASI	X	X	X				X	X
Pharmacokinetic data	X	X						
ADA	X	X						

ADA= anti-bimekizumab drug antibody; AE=adverse events; ECG= electrocardiogram; IMP= investigational medicinal product; Q4W= every four weeks; TFL= tables, figures, and listings.

aSelect tables presenting TEAEs by PS0016 randomized treatment group and Dose adjustment group, as defined in [Section 11.2.3](#).

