### **3.9 Changes to protocol-defined analyses**

Change from Baseline in physical examination is listed as a secondary safety variable, in [Section 2.2.1.2](#). Only whether the physical examination was performed and the date it was performed is recorded on the CRF. Thus no summaries for the change from Baseline in physical examination will be provided.”

For the continuous efficacy variables based on the change from Baseline (PASI, BSA, and HADS), imputation for missing values in the protocol is based on multiple imputation (MI) via the Markov Chain Monte Carlo (MCMC) method. However, due to the smaller sample size in PS0018 this may cause problems in the algorithm. For this reason and for consistency with the PS0016 SAP, imputation in PS0018 will instead be based on last observation carried forward (LOCF).

For the dose adjustment groupings, the single and multiple dose adjuster groupings will be combined for summary purposes, unless stated otherwise.

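### Concentrations are summarized by PS0016 arm only, so from PS0018 Week 16 the planned PK tables and mean plots can mix 160 mg and 320 mg and none describes 320 mg

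*SAP*

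**What the plan says.** Protocol 3.2 makes PK a secondary objective: "To assess PK of bimekizumab". Protocol 14.3 plans the analysis in one line: "Bimekizumab plasma concentrations will be summarized for each treatment at each scheduled visit". It does not say whether treatment means the PS0016 arm or the PS0018 dose.

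SAP 3.6 sets a default: "Treatment assignment for the SS and PK-PPS will be according to the actual treatment received in PS0018, unless stated otherwise in" the treatment-group table (the second of the two tables numbered 3–1). In that table the row "Pharmacokinetic data" has two marks. Read with SAP 9, these are the two PS0016 arms, with nothing under PS0018 dose, dose adjustment group or All Subjects. SAP 9 confirms this for the table ("Individual concentrations will be summarized by PS0016 randomized treatment group at each scheduled visit based on the PK-PPS") and for the geometric-mean profiles ("Both treatment groups (PS0016 randomized treatment groups) will be overlaid on the same plot").

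SAP 3.9 declares three changes from the protocol: physical examination, LOCF in place of multiple imputation, and the adjuster groups ("For the dose adjustment groupings, the single and multiple dose adjuster groupings will be combined for summary purposes"). PK is not among them.

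**The concern.** The PS0016 arms differ only in whether a third 320 mg injection was given at PS0016 Week 16. That matters at entry to PS0018 and then washes out. The PS0018 dose can differ between subjects from Week 12 on, and from then it drives concentration more and more. The planned grouping therefore separates subjects on the factor that is fading and pools them on the factor that is growing.

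The report would tabulate adverse events and exposure by PS0018 dose and PASI by adjuster group, with no summary concentration for 320 mg to set beside them. The later-visit geometric means, confidence intervals and geoCVs would describe an unstated mixture of doses.

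**Working it through.** The plan gives no figure to reproduce here. The check is one of timing, followed by an illustration of size.

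**Timing.** Protocol Table 5–1 takes PK samples at Baseline, Weeks 4, 8, 12, 16, 28, 40 and 48/withdrawal, and SFU, all before dosing. The first 320 mg injection in PS0018 can be given at Week 12, after that visit's sample. Weeks 4, 8 and 12 therefore reflect 160 mg plus PS0016 carry-over. Weeks 16, 28, 40, 48 and SFU, 5 of 8 post-baseline PK visits, can mix doses.

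**Inputs.** The half-life is 27.81 days (Protocol 2.2.1, single 160 mg sc dose in healthy subjects) and the dosing interval is 28 days. Assumptions: mono-exponential decline, linear PK extended to 320 mg, and a share p of an arm on 320 mg. No document gives p, so 0.1 to 0.4 is shown.

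**Trough ratio.** The fraction left after one interval is r = 2^(−28/27.81) = 0.4976. The 160 mg trough after n injections is proportional to S(n) = (1 − rⁿ)/(1 − r). For escalation at Week e, seen at Week t, the 320/160 ratio is R = 1 + S((t − e)/4)/S(t/4).

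- e = 12, t = 16: 1 + S(1)/S(4) = 1 + 1/1.8685 = 1.535
- e = 12, t = 28: 1 + S(4)/S(7) = 1 + 1.8685/1.9756 = 1.946
- e = 12, t = 40 and 48: 1.993 and 1.998
- Escalation at Week 36: 1.503 at Week 40, 1.877 at Week 48
- Up at Week 12, back to 160 mg at Week 36: 1.491 at Week 40, 1.121 at Week 48

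**Shift in the pooled geometric mean.** The factor is R^p, for p = 0.1, 0.2, 0.3, 0.4:

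- Week 16: +4.4%, +9.0%, +13.7%, +18.7%
- Week 28: +6.9%, +14.2%, +22.1%, +30.5%
- Week 48: +7.2%, +14.9%, +23.1%, +31.9%

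Subjects who escalate may have lower exposure to begin with. If theirs is 30% lower, the factor is (0.7R)^p: +0.7% to +2.9% at Week 16 and +3.4% to +14.4% at Week 48.

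**Spread.** With an assumed within-dose geoCV of 30% and a twofold ratio, the pooled geoCV is 37%, 42% and 45% for p = 0.1, 0.2 and 0.3.

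**PS0016 carry-over.** Add 2r^((E + t − d)/4 − 1) for each PS0016 injection at week d, with entry at PS0016 Week E. Week 20 is the earliest entry after a Week 16 dose; Week 28 is assumed to be the latest. The arm B/arm A trough ratio (E = 20, then E = 28) is:

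- Week 4: 1.84, 1.24
- Week 12: 1.14, 1.03
- Week 16: 1.06, 1.02
- Week 28: 1.01, 1.00

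Carry-over lowers the Week 16 dose ratio only slightly, to between 1.50 and 1.53.

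**SFU.** The SFU sample is 16 weeks after Week 48 for a completer, so r⁴ = 6.1% of the Week 48 trough remains. Pooling there matters only if values are quantifiable, and the LLOQ is not given.

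**The case against.** - **The grouping is stated openly.** SAP 3.6 allows exceptions, and the table and SAP 9 state this one. Protocol 14.3 is ambiguous, and no objective asks for PK at 320 mg separately: the dose-increase objective covers safety and tolerability only. A reader might infer that the SAP breaches the protocol. The documents do not support that. They support a possible reading of treatment as PS0018 dose, a SAP default that points the same way, and no explanation in SAP 3.9.
- **The PS0016 split has a reason.** Protocol 14.2.2 gives early PS0016 influence as the reason for showing laboratory, ECG and vital-sign data by PS0016 arm. The same logic fits PK at Weeks 4 to 12, so those outputs should stay. It has little force at Week 16 and none by Week 28.
- **Dose is visible elsewhere.** Listings flag 320 mg time points (SAP 3.1), and individual plots show the dose of each administration (SAP 10). With at most 45 subjects this helps, and it would be wrong to say that 320 mg concentrations cannot be seen. These are subject-level displays, however, not summaries.
- **Columns by dose are not clean either.** A subject returned to 160 mg at Week 36 still has 1.49 times the 160 mg trough at Week 40. The 320 mg column would mix ratios of about 1.50 to 1.99 at that visit, and its members were selected for inadequate response. This stands. It is why the nonadjuster group is needed as well, and why the 320 mg column must not be read as a dose comparison.
- **Size is conditional.** If few subjects escalate, or escalators have low exposure, the shift is small. This also stands.

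**Conclusion.** The point holds as a reporting gap for a secondary objective and should be fixed; it does not touch the primary safety analysis. As written, no planned PK table or mean plot describes 320 mg, and from Week 16 the arm means need not describe 160 mg.

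Under the stated assumptions (half-life 27.81 days, linear PK, escalation at Week 12 and continued, 10% to 40% on 320 mg), the pooled geometric mean is about 4% to 19% high at Week 16 and 7% to 32% high at Week 48. If escalators have 30% lower exposure, these are about 1% to 3% and 3% to 14%. Later escalation or return to 160 mg lowers the figures. Pooling is possible, not certain, because the share on 320 mg is unknown.

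A reader might extend the point to antibody data, since Protocol 14.4 uses the same wording ("Anti-bimekizumab antibody data will be summarized for each treatment at each scheduled visit"). Shared wording alone does not show a defect there, and none is claimed.

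A separate minor point: Protocol 14.2.2 specifies an overall column for laboratory, ECG and vital-sign changes from Baseline. The SAP treatment-group table and SAP 11.3 and 11.4 omit it without a note in SAP 3.9, although SAP 3.6 lists All Subjects in the PS0016 display and allows overall summaries where applicable.

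**What to change.** Keep the PS0016-arm PK outputs. From Week 16 add a by-visit concentration summary and geometric-mean plot, pooled over PS0016 arms, in two groupings:

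1. PS0018 dose at the injection preceding the sample (160 mg, 320 mg, All), derived from the administration records. The listing flag will not do: it starts on the day of the increase, so it labels that day's pre-dose sample as 320 mg.
2. The existing nonadjuster/adjuster groups, so that nonadjusters give an uncontaminated 160 mg profile.

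Footnote samples taken fewer than 3 injections after a dose change: about 50%, 25% and 12% of the difference remains after 1, 2 and 3 injections (r, r², r³). State that the 320 mg column holds subjects selected for inadequate response and is not a dose comparison. Define treatment for PK and record the grouping in SAP 3.9. Separately, restore the overall column for laboratory, ECG and vital-sign changes.

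The cost is one extra derivation and the added table and plot, with no new data. The 320 mg cells may be small. SAP 9 prints only n, minimum and maximum when n is 3 or fewer, or when more than a third of values are missing or not quantifiable. Full statistics therefore need at least 4 subjects at a visit (4/45 = 9% of the maximum enrolment). With an assumed log-scale SD of 0.3 to 0.5, the 95% CI for the geometric mean, exp(t × SD/√n) either way, is a factor of 1.6 to 2.2 at n = 4 and 1.3 to 1.5 at n = 9.
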